4.7.2 Sources for overall lesion response

The tumor-response related endpoints derivation is based on the sequence of overall lesion responses at each assessment/time point. In this study, the overall lesion response at a given assessment/time point will be provided from single source, i.e., investigator (local radiology) reported overall lesion responses. No blinded independent review committee (BIRC) is established for independent tumor assessments. Therefore the evaluation of tumor-response related endpoints will be based only on investigator assessments in this study.

4.7.3 BOIR calculations in patients with measurable brain metastases at baseline

A patient with measurable brain metastases at baseline is defined as a patient having at least one target lesion in the brain. Inclusion of response assessments based on lesion locations in the brain for each assessment, including baseline to identify whether patients have measurable brain metastases, uses the following list of terms collected based on investigator reported tumor data ('Lesion Location' collected on the [RECIST] eCRF pages):

- Brain
- CNS: Infratentorial
- CNS: Supratentorial
- Cerebral cortex
- Meninges
- Spinal cord
- CNS - not otherwise specified
- Leptomeningeal
- Cerebellum

For all lesion locations above, 'Lesion Type' should be 'Non-nodal' for the inclusion of response assessments. This list may be updated based on actual data of the lesion locations

CONFIDENTIAL - For Business Use Only

(and the description of lesion) at the time of analysis, as per scientific judgment of the medical expert. Especially when the lesion location is 'Other', the description of lesion will be considered.

The following steps will be taken to calculate the best overall intracranial response (BOIR) for patients with measurable brain metastases at baseline:

1. If only target lesion in brain and no non-target lesions in brain are identified at baseline, calculate the sum of the measured diameters from all target lesions in the brain (selected from list above), and use new lesions in brain (if any, based on the list) to derive responses per assessment. Non-target lesion response status is not considered since no non-target lesions were identified in the brain at baseline.
2. If both target and non-target lesions in the brain are identified at baseline, calculate the sum of the measured diameters from all target lesions in the brain (selected from list above), use all non-target lesion response status in the brain (selected from list above) and new lesions in the brain (if any, based on the list) to derive responses per assessment.
3. For each assessment, derive overall intracranial response.
4. For the whole set of derived overall intracranial responses, calculate BOIR.

For this subset of patients, calculate the OIRR.

4.7.4 Kaplan-Meier estimates

To analyze time-to-event endpoints (DOR, PFS and OS) an estimate of the survival function will be constructed using Kaplan-Meier (product-limit) method as implemented in PROC LIFETEST with METHOD=KM option (see example below). The median time to event and estimated event rates at different time points will be estimated, along with associated 95% two-sided CIs derived based on the complementary log-log transformation. This will be conducted via the SAS procedure LIFETEST. The TIME statement will include a variable with survival times (*survtime* in the example below) and a (right) censoring variable (*censor* in the example below) with a value of 1, representing censoring:

```
PROC LIFETEST DATA=dataset METHOD=KM CONFTYPE=LOGLOG;  
  TIME survtime*censor(1);  
  RUN;  
  /* survtime represents variable containing event/censor times;  
  censor represents censoring variable (1=censored, 0=event); */
```

Kaplan-Meier survival and failure function estimates from this procedure will be used to construct the Kaplan-Meier figures.

Median time to event will be obtained along with two-sided 95% CIs calculated from PROC LIFETEST output using the method of [Brookmeyer and Crowley, 1982](#).

Kaplan-Meier estimates with two-sided 95% CIs at specific time points will be summarized. The time points can be expressed in weeks or in months depending on the time-to-event endpoint. The CIs will be constructed using Greenwood's formula ([Collet, 1994, p.23](#)) for the standard error of the Kaplan-Meier estimate.

The Kaplan-Meier graphs will be constructed using SAS software.

CONFIDENTIAL - For Business Use Only

4.7.5 Confidence interval for response rate

ORR, DCR and OIRR will be summarized in terms of percentage rates with 95% CIs. An exact binomial confidence interval (implemented using SAS procedure FREQ with EXACT statement for one-way tables) will be calculated ([Clopper and Pearson, 1934](#)).

SAS procedure FREQ will be used to estimate the proportion of responders (binary outcome = 1 or 'Yes'), along with the associated 95% ($= 100 \times (1 - \text{two-sided alpha level of } 0.05)$) two-sided Pearson-Clopper CI. These estimates are obtained as follows:

```
PROC FREQ DATA=dataset;
  TABLE binary-event / BINOMIAL(LEVEL='Yes') ALPHA=0.05;
  EXACT BINOMIAL;
  RUN;
```

When there are no responders, SAS does not produce a CI by default. To obtain a CI in this situation, PROC FREQ is used as specified above except changing LEVEL='No'. From the results of this modified procedure, the values in percent of the lower confidence limit (LCL) and the upper confidence limit (UCL) of a 0% response rate are calculated as follows:

$$\text{LCL}_{\text{LEVEL}='Yes'} (\%) = 100\% - \text{UCL}_{\text{LEVEL}='No'} (\%),$$
$$\text{UCL}_{\text{LEVEL}='Yes'} (\%) = 100\% - \text{LCL}_{\text{LEVEL}='No'} (\%)$$

4.8 Safety evaluations

The text below gives more detailed instructions and rules needed for programming of the analyses described in [Section 2.8.2](#).

4.8.1 Multiple assessments within post-baseline visits

For all analyses regarding abnormal assessments or analyses based on worst or best post-baseline value (e.g., laboratory, ECGs, vital signs, ECOG performance status), all post-baseline values will be included (scheduled, unscheduled, repeat) unless otherwise specified. All unscheduled and repeat measurements will be included in listings.

Laboratory Data

Local laboratories will be used for laboratory evaluations in this study. However, if laboratory assessments are collected from both local and central laboratories on the same date, analyses are as follows. For shift tables using CTC grades to compare baseline to the worst post-baseline value, the assessment with worst post-baseline value is used for analyses irrespective of the source. For LFT summaries, where concurrent measurements are used in the calculation of number and percentage of patients with worst post-baseline values, the assessment with worst post-baseline value is used (since worst values are based on the largest ratio of lab value to its ULN for each patient) although the worst values for the different parameters may be coming from different laboratories.

ECGs

ECG data will be analyzed based on local laboratory reported results. At each scheduled time-pint, the triplicate ECGs will be taken as per protocol and the summary (mean) of their measurements for each ECG parameter will be collected in the [12 Lead ECG Evaluation – Local Analysis] eCRF page. Thus the mean of measurements associated with the scheduled time point will be used for the analyses.

4.8.2 Baseline

As defined in [Section 2.8.2](#), the last available assessment before or on the start date of study drug is defined as ‘baseline’ value or ‘baseline’ assessment.

Laboratory data

Local laboratories will be used for laboratory evaluations in this study. However, if both local and central laboratory assessments are performed on the same date and corresponding to the baseline assessment date, then the central laboratory assessment will be used for the calculation of baseline.

ECGs

Baseline for ECG measurement is the mean of the pre-dose replicate measurements on the baseline day. For the calculation of the mean, unscheduled assessments will not be combined with scheduled assessments. The mean will be calculated separately for scheduled and unscheduled. Note in this study the mean of replicate measurements at each time point is collected on the [12 Lead ECG Evaluation – Local Analysis] eCRF page and thus individual measurements are not entered in the database.

Study day 1 scheduled pre-dose ECGs will be considered to have been obtained prior to study drug administration. If a scheduled pre-dose measurement actually occurred post-dose, then the corresponding measurement will be treated and analyzed similar to an unscheduled post-dose measurement. Unscheduled assessments on study day 1 will be considered as post-baseline.

4.8.3 Laboratory parameters

This section provides further detail on the analysis of laboratory parameters that will be listed and summarized as described in [Section 2.8.2](#).

Handling of test values below LLOQ and above HLOQ

For numeric laboratory parameters, test values below the lower limit of quantification (LLOQ) and above the higher limit of quantification (HLOQ) may show ‘<n’ (or ‘<=n’) and ‘>n’ (or ‘>=n’) in the database respectively, where n can be any number. The classification of the CTC grades and the low/normal/high groups will follow a data handling rule: a value which shows ‘<n’ (or ‘<=n’) will be handled as zero; a value which shows ‘>n’ (or ‘>=n’) will be handled as n. These values will be presented in the listing as it is.

Hematology

Hematologic tests include hemoglobin, platelets, white blood cells (WBC), red blood cells (RBC), and differential counts (basophils, eosinophils, lymphocytes, monocytes, neutrophils (% or absolute).

The following rules will be applied to derive the WBC differential counts when only percentages are available (this is mainly for neutrophils and lymphocytes, because CTC grading is based on the absolute counts).

The method to convert the value is straightforward: for each patient, the original lab value (%) is divided by 100 and multiplied by WBC count, e.g., for neutrophils (NEU):

$$\text{NEU count} = (\text{WBC count}) \times (\text{NEU\%value} / 100)$$

In order to derive the corresponding absolute normal range, the rule to be applied depends on the availability of the % range and the absolute range for the differential:

- If absolute range is NOT missing (% range is or is not missing), then use the absolute range provided by the site.
- If % range is NOT missing and absolute range is missing, then the % normal limits (i.e., LLN and ULN) are divided by 100 and multiplied by the corresponding normal limits of WBC count, e.g., for neutrophils (NEU):

$$\text{LLN for NEU count} = (\text{LLN for WBC count}) \times (\text{LLN for NEU\%value} / 100),$$

$$\text{ULN for NEU count} = (\text{ULN for WBC count}) \times (\text{ULN for NEU\%value} / 100)$$

Biochemistry

The following calculation will be applied for corrected calcium (Ca) in SI unit:

Corrected Ca [mmol/L] = measured total Ca [mmol/L] + 0.02 x (40 – serum albumin [g/L]), where 40 represents the average albumin level in g/L.

The normal limits (LLN and ULN) for corrected Ca will also be derived using the above formula with the corresponding normal limits for total Ca and serum albumin.

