6.3.3 Criteria for LDK378 dose modifications

LDK378 dose reduction will follow the dose reduction steps described in [Table 6-2](#). For each patient, a maximum of 3 dose modifications is allowed after which the patient must be discontinued from treatment with LDK378. Once the dose of LDK378 has been reduced, it cannot be re-escalated. If a patient continues treatment with LDK378 after RECIST-defined PD as determined by the investigator, the criteria for dose modification will also apply.

Table 6-2 Dose reduction steps for LDK378

LDK378 dose levels	Dose* and schedule
Starting dose level	750 mg qd continuously
Dose level – 1	600 mg qd continuously
Dose level – 2	450 mg qd continuously
Dose level – 3	300 mg qd continuously **

*Dose reduction should be based on the worst preceding toxicity as per NCI-CTCAE version 4.03.

**Dose reduction below 300 mg/day is not allowed. If a dose reduction below 300 mg/day is required, the patient should be permanently discontinued from LDK378

Guidelines for dose interruptions and re-initiation of LDK378 treatment (with or without dose reduction) are described in [Table 6-3](#).

Table 6-3 Criteria for interruption and re-initiation of LDK378 treatment

Worst toxicity (CTCAE 4.03 Grade)*	Dose Modifications for LDK378
HEMATOLOGICAL	
Neutropenia (ANC: Absolute neutrophil count)	
Grade 1 (ANC < LLN - $1.5 \times 10^9/L$)	Maintain dose level
Grade 2 (ANC < 1.5 and $\geq 1.0 \times 10^9/L$)	
Grade 3 (ANC < 1.0 and $\geq 0.5 \times 10^9/L$)	
Grade 4 (ANC < $0.5 \times 10^9/L$)	Omit dose until resolved to \leq Grade 2, then: If resolved in \leq 7 days, then maintain dose level If resolved in $>$ 7 days, then \downarrow 1 dose level
Febrile neutropenia (ANC < $1.0 \times 10^9/L$, with a single temperature of $\geq 38.3^{\circ}C$ or a sustained temperature of $\geq 38^{\circ}C$ for more than one hour)	Omit dose until clinically resolved and neutropenia \leq Grade 2, then \downarrow 1 dose level
Thrombocytopenia	
Grade 1 (PLT < LLN - $75 \times 10^9/L$)	Maintain dose level
Grade 2 (PLT < 75 and $\geq 50 \times 10^9/L$)	
Grade 3 (PLT < 50 and $\geq 25 \times 10^9/L$)	Omit dose until resolved to \leq Grade 2, then: If resolved in \leq 7 days, then maintain dose level If resolved in $>$ 7 days, then \downarrow 1 dose level
Grade 4 (PLT < $25 \times 10^9/L$)	Omit dose until resolved to \leq Grade 2, then \downarrow 1 dose level
HEPATIC	
Alkaline phosphatase and/or Gamma-glutamyl transpeptidase (GGT)	

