7.2.2.5 Laboratory evaluations

Local laboratories will be used for the analysis of scheduled hematology, biochemistry and other blood specimens collected as part of safety monitoring (as detailed in [Table 7-1](#)). Dipstick urinalysis will also be performed locally. Laboratory values obtained during the Screening phase will be used to assess patient's eligibility. The time windows granted for laboratory evaluations are identical to the corresponding visit time windows for each visit (refer to [Section 7.1](#)).

Table 7-4 Local clinical laboratory parameters collection plan

Test Category	Test Name
Hematology	Hemoglobin, Platelets, Red blood cells, White blood cells with Differential (Basophils, Eosinophils, Lymphocytes, Monocytes, Neutrophils in percentage or absolute)
Chemistry	Albumin, ALT (SGPT), AST (SGOT), calcium, creatinine, creatinine clearance, total bilirubin, direct bilirubin (only if total bilirubin is \geq grade 2), blood urea nitrogen (BUN) or urea, magnesium, potassium, sodium, fasting glucose, phosphate(inorganic phosphorus), alkaline phosphatase, amylase, lipase, GGT
Urinalysis	Macroscopic Panel (Dipstick) (Color, bilirubin, Blood, Glucose, Ketones, pH, protein, specific gravity, urobilinogen) Microscopic panel (RBC, WBC, casts, crystals, bacteria, epithelial cells)
Coagulation	Pro-thrombin time (PT) and International normalized ratio (INR) or Quick Test
Pregnancy	At screening visit, serum pregnancy test At subsequent cycles, urinary pregnancy test.
Hormones (males only)	Testosterone (total and free), LH, Follicle-stimulating hormone (FSH)

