10.5.3.3 Laboratory abnormalities

For laboratory tests covered by the CTCAE version 4.03, the study's biostatistical and reporting team will grade laboratory data accordingly. For laboratory tests covered by CTCAE, a Grade 0 will be assigned for all non-missing values not graded as 1 or higher. In the unlikely case when a local laboratory normal range overlaps into the higher (i.e. non-zero) CTC grade, the laboratory value will still be taken as within normal limits and assigned a CTC grade of zero. Grade 5 will not be used.

For laboratory tests where grades are not defined by CTCAE, results will be graded by the low/normal/high classifications based on laboratory normal ranges.

The following summaries will be generated separately for hematology and biochemistry laboratory tests:

- shift tables using CTCAE grades to compare baseline to the worst on-treatment value

- for laboratory tests where CTCAE grades are not defined, shift tables using the low/normal/high/(low and high)

Listing of all laboratory data with values flagged to show the corresponding CTCAE grades and the classifications relative to the laboratory normal ranges will be generated.

A separate listing will display notable laboratory abnormalities (i.e., newly occurring CTCAE grade 3 or 4 laboratory toxicities).

[figure not shown]
[figure not shown]
In addition to the above mentioned tables and listings, other [REDACTED] analyses, for example figures plotting time course of raw or change in laboratory tests over time or box plots might be specified in the RAP.

[figure not shown]
[figure not shown]

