Local laboratories will be used for laboratory evaluations in this study. Laboratory data will be classified (by Novartis Oncology Statistical Programming personnel) into CTC grades according to the CTCAE version 4.03. For all reports, CTC grade is always obtained on the converted measurement in SI unit. Grade 5 will not be used. The CTC grade 0 will be assigned as below in different scenarios:

1. For laboratory parameters defined by criteria based on normal range only, a CTC grade of 0 will be assigned when the value is within normal limits.
2. For laboratory parameters whose grade is defined by criteria based on normal range and absolute values (e.g., platelet count decrease). A CTC grade of 0 will be assigned when the value is within normal limits.
3. For laboratory parameters whose grade is defined by criteria based on normal range and the change from baseline value with no other associated clinical criteria such as concomitant medication (e.g., creatinine increased), the following will be applied. For the grading of baseline value and for the grading of post-baseline values with missing baseline value, the grade will be derived using the criteria based only on the normal range as per CTCAE version 4.03. A CTC grade of 0 will be assigned when the post-baseline value is \leq ULN (for hyper) or \geq LLN (for hypo).

Laboratory parameters for which a grading does not exist will be classified into low/normal/high group by means of laboratory normal ranges.

As described previously, laboratory summary tables will include only laboratory assessments collected during the on-treatment period. Shift tables may use data from pre-treatment period for baseline calculations. The following summaries will be produced separately for the hematology and biochemistry (including hormones) laboratory data (by laboratory parameter):

- Shift tables using CTC grades to compare baseline to the worst post-baseline value for laboratory parameters with CTC grades.
- Shift tables using low, normal, high (as well as low and high combined) classifications to compare baseline to the worst post-baseline value for laboratory parameters where CTC grades are not defined.

The laboratory parameters listed in [Table 2-3](#) will be summarized as above stated. For bi-directional parameters, both hyper and hypo summaries will be presented.

Table 2-3 Laboratory parameters for summaries

Category	Parameter with CTC grades	Parameter without CTC grades

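### Where a site supplies only a percentage range, SAP 4.8.3 can derive a neutrophil lower limit below 1.5 ×10⁹/L, and the Grade 0 rule would then show some Table 6-3 Grade 2 counts as normal

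*SAP*

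**What the plan says.** Four provisions combine.

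- **Data collection.** Protocol Table 7-4 (section 7.2.2.5) lets the differential arrive as "Neutrophils in percentage or absolute", and local laboratories are used throughout.
- **Range derivation.** SAP 4.8.3 puts the laboratory's own range first: "If absolute range is NOT missing (% range is or is not missing), then use the absolute range provided by the site". The product rule applies only in the remaining case, "If % range is NOT missing and absolute range is missing", where "then the % normal limits (i.e., LLN and ULN) are divided by 100 and multiplied by the corresponding normal limits of WBC count". Neutrophils are the worked example, for both LLN and ULN.
- **Grade 0 rule.** SAP 2.8.2 covers parameters graded on a normal range plus absolute values in its second scenario: "e.g., platelet count decrease). A CTC grade of 0 will be assigned when the value is within normal limits". Neutrophils are not named there, but they are of this type, because Grade 1 in Table 6-3 runs from the LLN down to 1.5 ×10⁹/L and the higher grades have fixed cut-offs. Protocol 10.5.3.3 states the same override, introduced by "In the unlikely case when a local laboratory normal range overlaps into the higher" grade range.
- **Grade boundaries.** Protocol Table 6-3 has a row beginning "Grade 2 (ANC < 1.5 and", with a lower bound of 1.0 ×10⁹/L. Both that table and the SAP grade on CTCAE 4.03.

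**The concern.** A count is low when WBC and the neutrophil fraction are jointly low. The product of the two lower limits describes someone at the bottom of both ranges at once, which is rarer than being at the bottom of the range for the count itself. The derived LLN is therefore too low and the derived range too wide.

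For most purposes a slightly wide range is harmless. Here it feeds a rule that lets the range override a fixed cut-off. If the derived LLN is below 1.5, the Grade 1 band (LLN down to 1.5) is empty, and the upper part of the Grade 2 band is reported as Grade 0. For example, with a derived LLN of 1.32, a patient who falls from 1.6 to 1.4 would appear as Grade 0 to Grade 0 in the shift table, while 1.4 is Grade 2 in Table 6-3. In a safety set of about 20, each such patient is 1/20 = 5 percentage points of the table.

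**Working it through.** **Plan's own figure.** There is none to reproduce: neither document gives WBC or neutrophil-percentage limits. All limits below are assumptions.

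**Inputs from the documents.** Derived LLN = WBC LLN × NEU% LLN / 100 (SAP 4.8.3). Grade 2 is 1.0 to below 1.5 ×10⁹/L (Table 6-3). A value within limits is Grade 0 (SAP 2.8.2).

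**Step 1: when does the derived LLN fall below 1.5?** Setting WBC LLN × NEU% LLN / 100 < 1.5 gives NEU% LLN < 150 / WBC LLN. For 1.0, the bound is 100 / WBC LLN.

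| Assumed WBC LLN (×10⁹/L) | Derived LLN < 1.5 if NEU% LLN is below | Derived LLN < 1.0 if NEU% LLN is below |
|---|---|---|
| 3.0 | 50.0% | 33.3% |
| 3.3 | 45.5% | 30.3% |
| 3.5 | 42.9% | 28.6% |
| 4.0 | 37.5% | 25.0% |
| 4.5 | 33.3% | 22.2% |

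**Step 2: examples on both sides.**

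- 3.0 × 35 / 100 = 1.05: counts 1.05 to 1.49 become Grade 0.
- 3.3 × 40 / 100 = 1.32: counts 1.32 to 1.49 become Grade 0.
- 3.5 × 42 / 100 = 1.47: only 1.47 to 1.49 become Grade 0.
- 4.0 × 40 / 100 = 1.60: no Grade 2 count is affected.

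On a grid of the five WBC limits above by NEU% LLN of 35, 38, 40, 42, 45 and 50, 15 of 30 combinations give a derived LLN below 1.5 (1.05 to 1.485). The other 15 give 1.5 to 2.25. None is below 1.0. The grid is illustrative; the half-and-half split is not an estimate of how many sites are affected.

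**Step 3: is the product biased low?** Take the limits as 2.5th percentiles and suppose log WBC and log NEU% are roughly jointly normal, with standard deviations a and b and correlation r. The product of the limits lies 1.96(a + b) below the mean log count. The 2.5th percentile of the count lies only 1.96 × √(a² + b² + 2rab) below it. The first distance is larger unless r = 1.

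A simulation (2 million draws per range set, log-normal WBC, normal NEU%, ranges taken as central 95%) gives:

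| Assumed WBC; NEU% range | Product LLN | 2.5th percentile of count, r = 0 / 0.3 / 0.5 | % of values below product |
|---|---|---|---|
| 3.3–8.6; 38–75 | 1.254 | 1.625 / 1.492 / 1.414 | 0.32 / 0.81 / 1.23 |
| 3.5–9; 40–75 | 1.40 | 1.786 / 1.646 / 1.568 | 0.32 / 0.81 / 1.24 |
| 4–10; 40–70 | 1.60 | 1.997 / 1.858 / 1.774 | 0.32 / 0.81 / 1.24 |
| 4–11; 45–75 | 1.80 | 2.227 / 2.079 / 1.990 | 0.38 / 0.86 / 1.28 |

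The product cuts off about 0.3% to 1.3% of healthy values where a 95% range should cut off 2.5%. Where the product is 1.5 or above, no Grade 2 count is hidden, but the Grade 0/1 boundary is still placed too low.

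**The case against.** **The misgrading is conditional.** A reader might infer that the SAP will report Grade 2 neutropenia as normal. The documents do not support that. The site must supply a percentage range without an absolute one, and the product must be below 1.5. Table 7-4 permits percentages; it does not show that any site lacks an absolute range. This stands, and it limits the point to what the rule can do.

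**The override is protocol policy.** Protocol 10.5.3.3 knowingly lets a normal range outrank a CTC grade, and a laboratory-supplied LLN below 1.5 would have the same effect. In the first range set of the simulation, the 2.5th percentile itself is 1.492 or 1.414 at the two positive correlations. So SAP 4.8.3 does not create the override. But the protocol describes the overlap as unlikely and speaks of a local laboratory's range; a limit that the sponsor computes by a downward-biased formula is not one, and it makes the overlap more likely.

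**The reach is narrow.** A reader might also infer that serious neutropenia is hidden, that dosing is affected, or that lymphopenia is understated to a known degree. None of these follows. The separate abnormality listing covers Grades 3 and 4 and changes only if the derived LLN is below 1.0. All values are listed and box-plotted, so the counts remain visible. Nothing says the programmed grade drives dose decisions. Neutropenia is not among the adverse events of special interest. For lymphocytes the derivation is the same, but the documents give no lymphocyte grade cut-offs, so no size can be computed.

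**Conclusion.** The point holds in conditional form. SAP 4.8.3 uses a product that is biased low as a lower limit. When that product is below 1.5 ×10⁹/L, SAP 2.8.2 assigns Grade 0 to counts that Table 6-3 places in Grade 2. Two outputs are affected: the neutrophil CTC shift table and the grade flags in the full laboratory listing. No efficacy analysis is touched.

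The size depends on laboratory limits that the documents do not give: from no Grade 2 count (4.0 and 40%) to counts of 1.05 to 1.49 (3.0 and 35%). The direction of the bias rests on the limits being 2.5th percentiles and on WBC and neutrophil percentage being less than perfectly correlated, with roughly normal logs in the algebra. This is a modest defect, but it is a stated rule that can give a wrong grade in a safety table, and it is cheap to correct before database lock.

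**What to change.** In SAP 4.8.3 and 2.8.2:

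1. State that a range derived by the sponsor from percentage limits never overrides an absolute CTCAE cut-off, so neutrophil counts below 1.5 ×10⁹/L are graded on the absolute boundaries whatever the derived LLN.
2. Limit the Grade 0 override of protocol 10.5.3.3 to ranges supplied by the laboratory. This keeps the protocol's policy.
3. Where possible, obtain the site's absolute range and use it for the Grade 0/1 boundary. A fixed standard reference range for all sites is not needed.
4. Apply the same principle to other differentials graded on absolute counts, lymphocytes included.

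The cost is a short SAP edit and a small programming change, plus a request to any site without an absolute range. A few more Grade 1 or 2 values may be shown. Some between-site difference remains: a laboratory-supplied LLN below 1.5 will still yield Grade 0 for counts that are Grade 2 elsewhere. That follows from protocol 10.5.3.3, and this change does not alter it.

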Hematology	absolute lymphocytes [hyper, hypo]	basophils
	absolute neutrophils [hypo]	eosinophils
	hemoglobin [hypo]	monocytes
	platelet counts [hypo]	RBC
	WBC [hyper, hypo]	
Biochemistry	albumin [hypo]	blood urea nitrogen (BUN) or urea
	alkaline phosphatase [hyper]	direct bilirubin
	ALT (SGPT) [hyper]	

Category	Parameter with CTC grades	Parameter without CTC grades
	amylase [hyper] AST (SGOT) [hyper] corrected calcium* [hyper, hypo] creatinine [hyper] creatinine clearance [hypo] GGT [hyper] glucose [hyper, hypo] lipase [hyper] magnesium [hyper, hypo] phosphate (inorganic phosphorus) [hypo] potassium [hyper, hypo] sodium [hyper, hypo] total bilirubin [hyper]	
Hormones (males only)		follicle stimulating hormone (FSH) luteinizing hormone (LH) testosterone, free testosterone, total (free and bound)

*Corrected for albumin. See [Section 4.8.3](#) for details on calculation of parameter.

Laboratory parameters for urinalysis, coagulation and pregnancy listed below will be presented in listings and will not be summarized.

- Urinalysis: macroscopic panel (dipstick) (color, bilirubin, blood, glucose, ketones, pH, protein, specific gravity, urobilinogen), microscopic panel (RBC, WBC, casts, crystals, bacteria, epithelial cells).
- Coagulation: international normalized ratio (INR), pro-thrombin time (PT) or quick test.
- Pregnancy: serum pregnancy test, urinary pregnancy test.

The following listings will be produced for the laboratory data for all laboratory parameters.

- Listing of patients with laboratory abnormalities of CTC grade 3 or 4 (for laboratory parameters where CTC grades are defined)
- Listing of all laboratory data with values flagged to show the corresponding CTC grades and the classifications relative to the laboratory normal ranges.

In addition, laboratory normal ranges will be listed by laboratory identification number and laboratory category.

Box plot of laboratory data by time point (scheduled visit) will be produced for each of all laboratory parameters with the exception of qualitative data such as urine dipstick glucose.

Liver function tests

Liver function tests (LFTs) of interest for LDK378 are total bilirubin (TBILI), ALT, AST and alkaline phosphatase (ALP). In what follows, AT refers to ALT or AST values. LFTs will be summarized as follows:

- Shift tables of baseline vs. worst post-baseline values for the categories:

CONFIDENTIAL - For Business Use Only

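### SAP 4.8.3 does not say how calcium and albumin limits are paired when deriving corrected-calcium normal limits; the natural pairing makes the range too narrow and the opposite pairing too wide

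*SAP*

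**What the plan says.** SAP 4.8.3 (Biochemistry) defines corrected calcium in mmol/L as measured total calcium + 0.02 × (40 − serum albumin in g/L), "where 40 represents the average albumin level in g/L". The next sentence says that the LLN and ULN "for corrected Ca will also be derived using the above formula with the corresponding normal limits for total Ca and serum albumin". It does not state which albumin limit goes with which calcium limit.

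The Hematology part of the same section uses similar wording for neutrophils: percentage limits are "multiplied by the corresponding normal limits of WBC count". There the equations follow, with LLN paired with LLN and ULN with ULN.

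SAP 2.8.2 shows where the limits are used. Corrected calcium is a CTC-graded parameter in Table 2-3, in both directions, and "For bi-directional parameters, both hyper and hypo summaries will be presented". For parameters graded on the normal range, "a CTC grade of 0 will be assigned when the value is within normal limits"; the SAP repeats that condition for parameters graded on both the range and absolute values. The full listing has "values flagged to show the corresponding CTC grades and the classifications relative to the laboratory normal ranges".

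**The concern.** The neutrophil product rises in both of its inputs, so pairing lower with lower and upper with upper gives the extremes. Corrected calcium rises with total calcium but falls as albumin rises. The same pairing therefore offsets part of the calcium range instead of bounding the corrected value. A programmer who carries the neutrophil pattern down a few lines would obtain limits that are too tight. One who notices the minus sign and crosses the limits would obtain limits that are too loose.

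At stake is whether patients with ordinary calcium and albumin appear as hypo- or hypercalcaemic in the shift tables and listings, or whether mild abnormalities drop out of them. With about 20 patients, one misclassified patient is 1/20 = 5% of a table. The introduction to SAP Section 4 says these rules guide the programming and go into CSR Appendix 16.1.9, so whichever version is coded becomes the documented method.

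**Working it through.** **Inputs from the SAP:** the formula cCa = Ca + 0.02 × (40 − alb) and the reference of 40 g/L (4.8.3). **Not in the documents:** any calcium or albumin range, since local laboratories are used. All ranges below are assumptions. The plan states no resulting limits, so there is no figure of its own to reproduce.

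**Step 1. Same-limit pairing (as for neutrophils).**

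- LLN′ = LLN_Ca + 0.02 × (40 − LLN_alb)
- ULN′ = ULN_Ca + 0.02 × (40 − ULN_alb)
- Width′ = (ULN_Ca − LLN_Ca) − 0.02 × (ULN_alb − LLN_alb)

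The range narrows whatever the local limits are. If LLN_alb < 40 < ULN_alb, then LLN′ > LLN_Ca and ULN′ < ULN_Ca, so both limits move inward.

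**Step 2. Crossed pairing** (LLN_Ca with ULN_alb, ULN_Ca with LLN_alb).

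- Width″ = (ULN_Ca − LLN_Ca) + 0.02 × (ULN_alb − LLN_alb)

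The range widens by the same amount.

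**Step 3. Numbers.** Assume Ca 2.15–2.55 mmol/L and albumin 35–45 g/L.

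- Same-limit: 2.15 + 0.02 × 5 = 2.25 and 2.55 − 0.02 × 5 = 2.45. The width is 0.20 instead of 0.40.
- Crossed: 2.15 − 0.10 = 2.05 and 2.55 + 0.10 = 2.65. The width is 0.60.

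Other assumed ranges (width in brackets):

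| Ca | Albumin | Same-limit | Crossed |
|---|---|---|---|
| 2.15–2.55 (0.40) | 35–45 | 2.25–2.45 (0.20) | 2.05–2.65 (0.60) |
| 2.15–2.55 (0.40) | 35–50 | 2.25–2.35 (0.10) | 1.95–2.65 (0.70) |
| 2.15–2.55 (0.40) | 41–51 | 2.13–2.33 (0.20) | 1.93–2.53 (0.60) |
| 2.10–2.60 (0.50) | 35–50 | 2.20–2.40 (0.20) | 1.90–2.70 (0.80) |
| 2.20–2.50 (0.30) | 35–50 | 2.30–2.30 (0) | 2.00–2.60 (0.60) |

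**Step 4. A patient at the formula's own reference.** At albumin 40 the correction is zero, so corrected calcium equals total calcium. Take the first row.

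- Same-limit: total calcium of 2.20 or 2.50 is normal for the laboratory but falls below 2.25 or above 2.45, so it is flagged.
- Crossed: total calcium of 2.10 is below the laboratory's 2.15 but inside 2.05–2.65, so it is not flagged.

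**Step 5. How wide should the range be?** Suppose each reference range is the mean ± a fixed multiple of the SD, and let r be the calcium–albumin correlation. Then

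W² = W_Ca² + (0.02 W_alb)² − 2r × W_Ca × 0.02 W_alb.

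With W_Ca = 0.40 and 0.02 W_alb = 0.20, W² = 0.20 − 0.16r:

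- r = 1: √0.04 = 0.20, the same-limit width
- r = 0.25: √0.16 = 0.40, the unchanged total-calcium width
- r = 0: √0.20 = 0.45
- r = −1: √0.36 = 0.60, the crossed width

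Same-limit pairing is therefore right only under perfect positive correlation, and crossed pairing only under perfect negative correlation.

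**The case against.** The best defence is that the sentence is under-specified, not wrong: no equation is written, the pairing is borrowed from a different rule, and the direction of any error is not fixed by the text. It is correct that the pairing is inferred. A reader might conclude that the SAP definitely narrows the range, and the text does not support that. But the ambiguity does not rescue the rule, because step 5 shows that both available pairings fail except at the extremes of correlation.

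A second defence has more substance. If calcium and albumin are positively correlated, corrected calcium can vary less than total calcium, so some narrowing may be legitimate. Both pairings also centre the range at the calcium midpoint + 0.02 × (40 − albumin midpoint), which is where corrected values should centre. This stands. The criticism is of the full amount of narrowing, not of any narrowing.

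Third, the consequence is small and traceable: "laboratory normal ranges will be listed by laboratory identification number and laboratory category", so a reader of the listings could detect a misflag. This also stands.

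Protocol 10.5.3.3 offers little to either side. Its statement that "the laboratory value will still be taken as within normal limits and assigned a CTC grade of zero" is about a local range that overlaps a higher CTC grade, not about limits derived by formula.

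Stronger readings to resist:

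- **Eligibility.** Inclusion criterion 11 does refer to albumin-corrected calcium, but it is applied to laboratory values before the first dose; the SAP sentence is a reporting rule.
- **Masked deterioration.** Low and high are summarized separately, so a false low at baseline can mask only a shift from grade 0 to 1 on the low side.
- **A misflag rate for this trial.** None can be stated without the local ranges and the correlation.

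**Conclusion.** The point holds as a minor one. The derivation of corrected-calcium limits in SAP 4.8.3 is unsound under either pairing: too narrow under the natural, inferred one and too wide under the other, by exactly 0.02 × (ULN_alb − LLN_alb) mmol/L in each case. That result is algebra on the SAP's own formula and needs no outside data. The size in mmol/L depends on local ranges that the documents do not give; for assumed albumin widths of 10 to 15 g/L it is 0.20 to 0.30 mmol/L.

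The reach is limited to grade 0 versus mild abnormality, and the range flags, for one parameter in descriptive shift tables and listings. No effect on ORR or any other efficacy endpoint, on eligibility or on grade 3/4 reporting is claimed.

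**What to change.** Replace the sentence in SAP 4.8.3 on the corrected-calcium limits with:

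> Corrected Ca will be graded against the laboratory's normal limits (LLN, ULN) for total calcium.

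This is what the formula returns at its own reference of 40 g/L. Describe it as an approximation and add a table footnote:

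> The correction uses a fixed albumin reference of 40 g/L; where a laboratory's albumin range is centred above 40 g/L, low flags may be over-reported and high flags under-reported, and the reverse where it is centred below 40 g/L.

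An equally short alternative avoids that shift: move both total-calcium limits by 0.02 × (40 − midpoint of the laboratory's albumin range). This keeps the width and centres the range correctly. With the assumed Ca 2.15–2.55, albumin 35–45 gives no shift and the two options coincide; albumin 35–50 (midpoint 42.5) gives a shift of −0.05 and limits of 2.10–2.50.

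The cost is one SAP sentence, one footnote and one line of code, settled before programming. The downside is that the limits remain approximate under either option, because the true width depends on a correlation that the plan does not have.
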